8.3.10. Medication Errors

Medication errors may result from the administration or consumption of the study intervention by the wrong participant, or at the wrong time, or at the wrong dosage strength.

Exposures to the study intervention under study may occur in clinical trial settings, such as medication errors.

Safety Event	Recorded on the CRF	Reported on the CT SAE Report Form to Pfizer Safety Within 24 Hours of Awareness
Medication errors	All (regardless of whether associated with an AE)	Only if associated with an SAE

Medication errors include:

- Medication errors involving participant exposure to the study intervention;
- Potential medication errors or uses outside of what is foreseen in the protocol that do or do not involve the study participant.

Such medication errors occurring to a study participant are to be captured on the medication error page of the CRF, which is a specific version of the AE page.

In the event of a medication dosing error, the sponsor should be notified immediately **within 24 hours**.

Whether or not the medication error is accompanied by an AE, as determined by the investigator, the medication error is recorded on the medication error page of the CRF and, if applicable, any associated AE(s), serious and nonserious, are recorded on the AE page of the CRF.

Medication errors should be reported to Pfizer Safety within 24 hours on a CT SAE Report Form **only when associated with an SAE.**

8.4. Treatment of Overdose

For this study, any dose of study intervention greater than one dose within a 12-hour time period will be considered an overdose.

The maximum surface area of administration is 22% BSA for AD and 16.5% for psoriasis participants. Investigators should be aware that administration to significantly greater area may also be treated as an overdose at Investigator discretion.

The Sponsor does not recommend specific treatment for an overdose.

In the event of an overdose, the investigator should:

1. Contact the medical monitor within 24 hours.
2. Closely monitor the participant for any AEs/SAEs and laboratory abnormalities for at least 28 calendar days after the overdose of study intervention.
3. Document the quantity of the excess dose as well as the duration of the overdose in the CRF.
4. Overdose is reportable to Safety **only when associated with an SAE.**

CCI

Decisions regarding dose interruptions or modifications will be made by the investigator in consultation with the medical monitor based on the clinical evaluation of the participant.

CCI

CCI

CCI

CCI

8.9. Immunogenicity Assessments

Immunogenicity assessments are not included in this study.

8.10. Health Economics

Health economics/medical resource utilization and health economics parameters are not evaluated in this study.

9. STATISTICAL CONSIDERATIONS

Detailed methodology for summary and statistical analyses of the data collected in this study is outlined here and further detailed in a SAP, which will be maintained by the sponsor. The SAP may modify what is outlined in the protocol where appropriate; however, any major modifications of the primary endpoint definitions or their analyses will also be reflected in a protocol amendment.

9.1. Estimands and Statistical Hypotheses

9.1.1. Estimands for AD

The primary estimand will be the population average treatment effect on percent change from baseline in EASI score relative to vehicle at 6 weeks in the absence of prohibited medication without regard to compliance. All observations after the initiation of prohibited medication will be set to missing. Missing data from all causes, including post-randomization prohibited medication use will be imputed in the PF-07038124 arms using a copy to control method (ie, missing data in 0.01% QD regimen will be imputed from the distribution of participants on QD vehicle). Participants with inadequate compliance will have their recorded EASI scores used as is in the analysis. The population-based treatment effect will be the differences in the mean change from baseline in treatment arm compared to the vehicle.

The secondary estimand will be the estimated population average treatment effect on the rates of IGA response (participants with a score of 0 or 1 and a 2 point or greater decrease from baseline) at Week 6 relative to vehicle without regard to compliance with IP in the absence of prohibited medication. This is a composite estimand where success is defined as achievement of an IGA response as defined above while remaining on study, providing data and not taking prohibited medication; lack of compliance or adverse events will not be counted as a failure. The population-based treatment effect will be the differences in the proportions of success in each treatment arm compared to the corresponding vehicle. EASI 75 and other EASI scores will be treated in a similar manner.

All other secondary continuous clinical endpoints will be analyzed using the primary estimand, while all other secondary categorical clinical endpoints will be analyzed using the secondary estimand described above. CCI

Other estimands may be used for some of the primary and secondary endpoints as a means to examine the robustness of the results and to compare to available literature as needed. Details of these analyses will be presented in the Statistical Analysis Plan (SAP).

9.1.2. Estimands for Psoriasis

The primary estimand will be the population average treatment effect on change from baseline in PASI scores at Week 6 relative to vehicle without regard to compliance in the absence of prohibited medication. Measurements after the initiation of prohibited medication will be censored and treated as missing data. Missing data due to censoring, study withdrawal or other reasons will have data imputed using a copy to control method (ie, missing data in 0.01% QD regimen will be imputed from the distribution of participants on QD vehicle) assuming these participants no longer receive an efficacy benefit from the IP but rather, have a response similar to participants assigned to vehicle. Participants with inadequate compliance will have their recorded PASI scores used as is in the analysis. The population-based treatment effect will be the differences in the mean change from baseline in each treatment arm compared to the corresponding vehicle.

The secondary estimand will be the population average treatment effect on the PGA response rate (percentage of participants with a score of clear (0) or almost clear (1) and ≥ 2 point improvement from baseline at Week 6 relative to vehicle without regard to compliance with IP in the absence of prohibited medication. This is a composite estimand where success is defined as achievement of a PGA response while remaining on study, providing data and not taking prohibited medication; lack of compliance or adverse events will not be counted as a failure. The population-based treatment effect will be the differences in the proportions of successes in each treatment arm compared to the corresponding vehicle.

All other key secondary continuous clinical endpoints will be analyzed using the primary estimand, while all other key secondary categorical clinical endpoints will be analyzed using the secondary estimand described above. CCI

Other estimands may be used for some of the primary and secondary endpoints as a means to examine the robustness of the results and to compare to available literature as needed. Details of these analyses will be presented in the SAP.

9.2. Sample Size Determination

9.2.1. Sample Size Determination for AD

The sample size calculation is based on the primary endpoint (percentage change from baseline in EASI score at Week 6). A total of 56 randomized participants in 1 treatment group and 1 vehicle group (28/arm) will provide approximately 90% power to detect a difference of 50 in percentage change from baseline with a common standard deviation 48% between PF-07038124 and a vehicle arm, controlling the two-sided error rate alpha 0.05. These calculations allow for a 25% dropout rate leaving 42 evaluable participants (21/arm).

For the key secondary endpoint, IGA response rate of clear or almost clear and ≥ 2 points improvement at Week 6, assuming 20% rate for vehicle and 55% rate for the treatment, this sample size provides 66% power controlling the two-sided error rate alpha 0.05.

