9.2.2. Sample Size Determination for Psoriasis

The sample size is based on the primary efficacy endpoint, PASI change from baseline at Week 6. With an assumed standard deviation of 4.2 and treatment difference of 4.5, a total of 32 randomized participants in 2 treatment groups (16/arm) will provide approximately 80% power for the comparison of active versus vehicle group at a two-sided significance of 0.1. This calculation allows for an approximate 25% dropout rate, that is 12 participants evaluable per arm at Week 6, where evaluable is defined as included in the mITT set (defined in [Section 9.3](#)).

For the key secondary endpoint, PGA response rate of clear or almost clear and ≥ 2 points improvement at Week 6, assuming 20% rate for vehicle and 65% rate for the treatment, this sample size provides 61.9% power controlling the two-sided error rate alpha 0.05.

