9.4.1. Efficacy Analyses for AD

Endpoint	Statistical Analysis Methods
Primary: Percent Change from Baseline EASI at Week 6	A landmark analysis using analysis of covariance of percent change from baseline in EASI, adjusting for the baseline EASI score, to estimate the effect of the initially randomized treatment in the absence of prohibited medication regardless of treatment compliance. The analysis will use the mITT analysis set. Missing data due to any cause including censoring due to initiation of prohibited medication will be imputed using the corresponding vehicle arm, missing data in a vehicle arm will be imputed using data from the vehicle arm assuming data are missing at random (MAR). The analysis will combine the results from the multiple imputations using Rubin's rule as implemented in SAS PROC MIANALYZE.
Secondary: IGA Response at Week 6	A landmark analysis of the composite endpoint; achieving IGA without prohibited medication, while remaining on study and providing data. The analysis will use the mITT analysis set. Based on the definition of the composite endpoint all participants in the mITT set will have a response for all visits (ie, there is no missing data). The proportions responding and

Endpoint	Statistical Analysis Methods
	the corresponding risk difference comparing active treatment arm to vehicle group will be analyzed using the unconditional exact method; the risk differences and the corresponding 2-sided unconditional exact 90% confidence intervals will be computed using Chan and Zhang (1999) ¹⁶ method.

CCI

Other continuous secondary endpoints at time points specified in the SoA including change from baseline EASI, will be analyzed as described for the primary estimand along with descriptive statistics and possibly graphical displays.

Other binary secondary endpoints at time points specified in the SoA including, CCI EASI 75, CCI IGA of clear or almost clear will be analyzed as described for the secondary estimand along with descriptive statistics and possibly graphical displays.

CCI

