## **5.2. General Methods**

### **5.2.1. Analyses for Binary Endpoints**

Landmark (cross-sectional) analyses of key binary endpoints will be analyzed by first treating missing data as non-responders and then applying Chan and Zhang's exact confidence interval (CI) method.

For all binary endpoints, a summary based on the mITT of the number of subjects in each category based on observed cases in each treatment arm at each time point will be produced and the response rate will also be plotted against time, by treatment group.

CCI

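### The stated 66% (IGA) and 61.9% (PGA) power come from a normal approximation on completers and do not match the planned exact, non-responder mITT analysis under either reading of the assumed rates

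*Protocol*

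**What the plan says.** Protocol 9.2.1 sizes the AD part on EASI. "A total of 56 randomized participants in 1 treatment group and 1 vehicle group (28/arm") are planned, and "These calculations allow for a 25% dropout rate leaving 42 evaluable participants (21/arm"). It then gives power for IGA response, the Week 6 key secondary endpoint: "assuming 20% rate for vehicle and 55% rate for the treatment, this sample size provides 66% power controlling the two-sided error rate alpha 0.05". Protocol 9.2.2 does the same for PGA response in psoriasis, with 16 randomised and 12 evaluable per arm: "assuming 20% rate for vehicle and 65% rate for the treatment, this sample size provides 61.9% power", again at two-sided 0.05. It describes those 12 as the participants in the mITT set. SAP 5.1 repeats both paragraphs. Neither document names the test behind the two power figures, or says whether the response rates refer to completers or to everyone dosed.

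The analysis is specified elsewhere.

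- **Analysis set.** Protocol 9.3 and SAP 4 define mITT as everyone randomised who applies at least one dose.
- **Dropouts.** Protocol 9.1.1 and 9.1.2 define a composite endpoint in which success requires staying on study and providing data. SAP 5.2.1 describes "first treating missing data as non-responders and then applying" the Chan-Zhang method. SAP 5.3.1 makes one exception: visits missed because of COVID-19 are excluded, not counted as failures.
- **Method.** Protocol 9.4.1 says the proportions and risk difference "will be analyzed using the unconditional exact method", with two-sided 90% intervals. Protocol 9.4.2 and SAP 6.2.1.1 agree.

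**The concern.** A power statement should describe the analysis that will be run. Here the analysis set, the handling of dropouts and the test in the power calculation all appear to differ from those in the analysis section, and the alpha differs from the level of the reported interval. The protocol calls IGA and PGA response key secondary endpoints. Anyone weighing a result that is not significant will ask what chance the study had of showing the assumed effect, and the two published figures may not answer that.

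**Working it through.** **Inputs.** IGA: 20% against 55%, 28 randomised and 21 evaluable per arm (Protocol 9.2.1). PGA: 20% against 65%, 16 randomised and 12 evaluable per arm (Protocol 9.2.2). Dropout is 25% and two-sided alpha 0.05 in both.

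**Step 1: reproduce the stated figures.** Pooled-variance normal approximation without continuity correction:

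power = Φ{ [d − 1.96·√(2p̄(1−p̄)/n)] / √[(p₁(1−p₁) + p₀(1−p₀))/n] }

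- IGA, n = 21, d = 0.35, p̄ = 0.375: (0.35 − 1.96 × 0.1494)/0.1393 = 0.410, so power is 65.9%. Stated: 66%.
- PGA, n = 12, d = 0.45, p̄ = 0.425: (0.45 − 1.96 × 0.2018)/0.1797 = 0.303, so power is 61.9%. Stated: 61.9%.

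Other methods on the same n fit less well (IGA / PGA): unpooled 71.0% / 70.7%; continuity-corrected 52.7% / 43.6%; arcsine 67.4% / 64.2%; Fisher 52.8% / 49.9%; unconditional exact 62.8% / 59.1%. Of the methods tried, only the pooled approximation on completers matches both figures closely.

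**Step 2: the planned test.** All 2×2 outcomes were enumerated and ordered by the pooled score statistic. The tail probability was maximised over the common response rate, and the null of zero difference was rejected at 0.025 per side. This is the Chan-Zhang test at difference zero.

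**Step 3: the planned set and dropout rule.** If the rates are completer rates and 25% of each arm become failures, each rate is multiplied by 0.75:

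- IGA: 0.75 × 55% = 41.25% against 0.75 × 20% = 15%, n = 28.
- PGA: 0.75 × 65% = 48.75% against 15%, n = 16.

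If the rates already count dropouts as failures, they apply unchanged to 28 and 16.

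| Scenario | Alpha (two-sided) | IGA | PGA |
|---|---|---|---|
| Stated | 0.05 | 66% | 61.9% |
| Exact, completers only (21, 12) | 0.05 | 62.8% | 59.1% |
| Normal approximation, dropouts as failures (28, 16) | 0.05 | 59.3% | 53.8% |
| Exact, completer rates, dropouts as failures (28, 16) | 0.05 | 59.2% | 52.3% |
| Exact, rates already include dropouts (28, 16) | 0.05 | 77.5% | 73.5% |
| Exact, completer rates, dropouts as failures (28, 16) | 0.10 | 69.4% | 62.2% |

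**Step 4: source of the difference.** Changing only the test, on completers, costs 65.9 − 62.8 = 3.1 points (IGA) and 61.9 − 59.1 = 2.8 points (PGA). Changing only the dropout rule and n, within the normal approximation, costs 65.9 − 59.3 = 6.6 and 61.9 − 53.8 = 8.1 points. On the completer-rate reading, most of the loss comes from the dropout rule.

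**The case against.** The strongest reply is that 59% and 52% are not the power of the planned analysis either. The plan reports 90% intervals for these endpoints, and SAP 5.1 confines statistical inference to EASI and PASI. A 90% interval excluding zero corresponds to two-sided 0.10. At that level, with completer rates and dropouts as failures, exact power is 69.4% and 62.2%, at or slightly above the stated values. This stands as a limit on any claim of a shortfall. It does not rescue the text, which specifies 0.05; it adds alpha to the list of things to reconcile.

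Second, 25% is a planning allowance. Participants who stop treatment stay in the study (Protocol 7.1), IGA and PGA are collected at early termination, the Week 6 window runs from day 37 to day 57 (SAP Appendix 2.1), and COVID-19 missingness is excluded. Fewer than 25% might therefore be imputed as failures. With an assumed 15%, exact power at 0.05 is 67.0% and 61.1%, close to the stated figures. That is a fair sensitivity case, but 15% is not in the documents and 25% is.

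Third, Protocol 9.2.2 equates the 12 evaluable per arm with the mITT set; on 12 per arm the exact figure is 59.1%, only 2.8 points below that stated. But the mITT definition in 9.3 removes nobody for leaving after a first dose, so the equation contradicts the protocol's own definition.

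A reader might infer that power is overstated by 7 and 10 points, or that the sponsor miscalculated. The documents support neither. The arithmetic is right for the calculation performed, and the size and direction of the mismatch depend on what the assumed rates mean.

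**Conclusion.** The point holds in this form: the stated powers belong to a completer calculation by normal approximation, not to the planned exact analysis of all dosed participants. At two-sided 0.05 and 25% dropout in both arms, the planned analysis has about 59% (IGA) and 52% (PGA) power if the rates are completer rates. That is 66 − 59.2 = 6.8 and 61.9 − 52.3 = 9.6 points below the stated figures. If the rates are already composite, it has about 77.5% and 73.5%, which is 11.5 and 11.6 points above. Neither reading gives the stated numbers.

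The close match on 21 and 12 per arm suggests completer rates, but that is an inference. The exact figures also assume that everyone randomised is dosed, that every dropout is counted as a failure, and that none is excluded as COVID-19 missingness.

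The consequence is limited. These are secondary endpoints, EASI and PASI set the sample size, and the decision rule in SAP 5.1 does not use IGA or PGA. What is affected is how a non-significant IGA or PGA result should be read.

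**What to change.** In Protocol 9.2.1, 9.2.2 and SAP 5.1:

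1. State whether 20%, 55% and 65% count dropouts as failures.
2. State the alpha that matches the reported interval: keep 0.05 and explain the 90% interval, or move the power basis to 0.10.
3. Name the test and the n, and restate both powers from the unconditional exact test on 28 and 16 per arm. At 0.05 these are about 59% and 52% for completer rates, or 77.5% and 73.5% for composite rates. At 0.10 with completer rates they are about 69% and 62%.
4. Correct the statement in 9.2.2, repeated in SAP 5.1, that the 12 evaluable per arm are the mITT set.
5. Note that COVID-19 exclusions would reduce both n and the number of imputed failures.

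The cost is a text change and a short calculation. No participants are added and no analysis changes.

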9.2.2. Sample Size Determination for Psoriasis

The sample size is based on the primary efficacy endpoint, PASI change from baseline at Week 6. With an assumed standard deviation of 4.2 and treatment difference of 4.5, a total of 32 randomized participants in 2 treatment groups (16/arm) will provide approximately 80% power for the comparison of active versus vehicle group at a two-sided significance of 0.1. This calculation allows for an approximate 25% dropout rate, that is 12 participants evaluable per arm at Week 6, where evaluable is defined as included in the mITT set (defined in [Section 9.3](#)).

For the key secondary endpoint, PGA response rate of clear or almost clear and ≥ 2 points improvement at Week 6, assuming 20% rate for vehicle and 65% rate for the treatment, this sample size provides 61.9% power controlling the two-sided error rate alpha 0.05.

9.3. Analysis Sets

For purposes of analysis, the following analysis sets are defined:

Population	Description
Safety Analysis Set	All participants randomly assigned to IP and who apply at least 1 dose of IP. Participants will be analyzed according to the product they actually have received.

Defined Population for Analysis	Description
Modified Intention to Treat (mITT)	All participants randomly assigned to IP and who apply at least 1 dose of IP.

CCI

9.4. Statistical Analyses

The SAP will be developed and finalized before any analyses are performed and will describe the analyses and procedures for accounting for missing, unused, and spurious data. This section is a summary of the planned statistical analyses of the primary and secondary endpoints.

9.4.1. Efficacy Analyses for AD

Endpoint	Statistical Analysis Methods
Primary: Percent Change from Baseline EASI at Week 6	A landmark analysis using analysis of covariance of percent change from baseline in EASI, adjusting for the baseline EASI score, to estimate the effect of the initially randomized treatment in the absence of prohibited medication regardless of treatment compliance. The analysis will use the mITT analysis set. Missing data due to any cause including censoring due to initiation of prohibited medication will be imputed using the corresponding vehicle arm, missing data in a vehicle arm will be imputed using data from the vehicle arm assuming data are missing at random (MAR). The analysis will combine the results from the multiple imputations using Rubin's rule as implemented in SAS PROC MIANALYZE.
Secondary: IGA Response at Week 6	A landmark analysis of the composite endpoint; achieving IGA without prohibited medication, while remaining on study and providing data. The analysis will use the mITT analysis set. Based on the definition of the composite endpoint all participants in the mITT set will have a response for all visits (ie, there is no missing data). The proportions responding and

Endpoint	Statistical Analysis Methods
	the corresponding risk difference comparing active treatment arm to vehicle group will be analyzed using the unconditional exact method; the risk differences and the corresponding 2-sided unconditional exact 90% confidence intervals will be computed using Chan and Zhang (1999) ¹⁶ method.

CCI

Other continuous secondary endpoints at time points specified in the SoA including change from baseline EASI, will be analyzed as described for the primary estimand along with descriptive statistics and possibly graphical displays.

Other binary secondary endpoints at time points specified in the SoA including, CCI EASI 75, CCI IGA of clear or almost clear will be analyzed as described for the secondary estimand along with descriptive statistics and possibly graphical displays.

CCI

9.4.2. Efficacy Analyses for Psoriasis

Endpoint	Statistical Analysis Methods
Primary: Change from Baseline PASI at Week 6	A landmark analysis using analysis of covariance of change from baseline PASI, adjusting for the baseline PASI score, to estimate the effect of the initially randomized treatment in the absence of prohibited medication regardless of treatment compliance. The analysis will use the mITT analysis set. Missing data due to any cause including censoring due to initiation of prohibited medication will be imputed using the corresponding vehicle arm, missing data in a vehicle arm will be imputed using data from the vehicle arm assuming data are missing at random (MAR). The analysis will combine the results from the multiple imputations using Rubin's rule as implemented in SAS PROC MIANALYZE.
Secondary: PGA Response at Week 6	A landmark analysis of the composite endpoint; achieving a PGA response (a score of clear (0) or almost clear (1) and ≥ 2 point improvement from baseline) without prohibited medication, while remaining on study and providing data. The analysis will use the mITT analysis set. Based on the definition of the composite endpoint all participants in the mITT set will have a response for all visits (ie, there is no missing data). The proportions responding and the risk difference between treated arms and their corresponding vehicle control arm will be analyzed using an unconditional exact method: risk differences and corresponding 2-sided unconditional exact 90% confidence intervals will be computed using the

Endpoint	Statistical Analysis Methods
	Chan and Zhang (1999) ¹⁶ method.

CCI

Other continuous secondary endpoints at time points specified in the SoA including: absolute PASI, change from baseline PASI, percent change from baseline PASI, absolute and change from baseline Itch Severity Score, absolute and change from baseline Psoriasis Symptom Inventory will be analyzed as described for the primary estimand along with descriptive statistics and possibly graphical displays.

Other binary secondary endpoints at time points specified in the SoA including, CCI PASI 75, CCI PGA of clear or almost clear will be analyzed as described for the secondary estimand along with descriptive statistics and possibly graphical displays.

CCI

